#### 7.4.4 Subject Compliance Monitoring

The Anesthesiologist will verify that the label on the study drug that they receive in the operating room matches the study ID and initials on the subject's study ID bracelet.

#### 7.4.5 Blinding of the Test Article

The pharmacy will prepare solutions of ketamine alone, ketamine plus magnesium and plain normal saline in similar looking containers. In order to maintain the blind, each study patient will receive 2 IV infusions (see Section 7.4.2).

## 7.4.6 Receiving, Storage, Dispensing and Return

### 7.4.6.1 Receipt of Test Article

The study drugs are already in hospital formulary.

### 7.4.6.2 Storage

The investigational pharmacy will handle storage and distribution of study drugs according to their approved handling protocols.

### 7.4.6.3 Preparation and Dispensing

The pharmacy will prepare solutions of ketamine alone, ketamine plus magnesium and plain normal saline in similar looking containers. The containers will be labeled with the participant's study number and initials. In order to maintain the blind, each patient will receive 2 IV infusions. All patients will receive an IV bag with either 2 grams of Magnesium diluted in Normal Saline or Normal Saline alone and an IV containing Ketamine at a concentration of 1 mg/mL or 2mg/mL once diluted in Normal Saline or Normal Saline alone. Once prepared, the investigational pharmacy will deliver the bags to the OR window, or the drug will be picked up by the coordinator at the investigational pharmacy.

Following securement of the endotracheal tube, the study medication will be administered by the anesthesiologist over 10 minutes via an IV infusion pump.

### 7.4.6.4 Return or Destruction of the Test Article

Study drug will be discarded as per usual procedures.

### 7.4.6.5 Prior and Concomitant Therapy

Not applicable as we are using standard of care protocols.

## 8.0 Data and Specimen Banking For Future Undetermined Research

Not applicable.

## 9.0 Statistical Plan

### 9.1 Sample size determination

Up to 250 subjects will be enrolled in order to obtain enough data to determine if a significant difference exists between the treatment groups. This number will allow exclusions and withdrawals, in order to obtain the goal of 36 completed subjects per group.

Based on the Martinez study, the mean (and standard deviation) for the 48-hour morphine use in the ketamine group was 52 mg + 22 mg. Assuming that magnesium would yield a similar result as ketamine, a conservative expectation for the combination of ketamine and magnesium is a 25% reduction for the 24-hour morphine use to 19.5 mg. In order to achieve 80% statistical power with one-sided, 0.05 statistical tests, a sample size of 36 for each of the three groups is needed (total sample size of 108 completed patients for statistical analysis).

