## **1.0 Objectives**

### **1.1 Study Objectives**

The goal of our research proposal would be to determine if intra-operative ketamine and magnesium decrease the amount of opiate use in the first 24 hours after laparoscopic bariatric surgery.

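### Does sizing a 24-hour endpoint from a 48-hour mean and SD leave the 36 per group and 80% power in Section 9.1 without support?

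*Combined protocol and SAP*

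**What the plan says.** Section 1.1 sets the aim over one day: "determine if intra-operative ketamine and magnesium decrease the amount of opiate use in the first 24 hours after laparoscopic bariatric surgery". Section 1.2 makes hydromorphone use over the same 24 hours the primary endpoint.

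Section 9.1 starts from a cited study and a two-day window: "the mean (and standard deviation) for the 48-hour morphine use in the ketamine group was 52 mg + 22 mg". It then moves to one day: "a conservative expectation for the combination of ketamine and magnesium is a 25% reduction for the 24-hour morphine use to 19.5 mg". The size follows: "In order to achieve 80% statistical power with one-sided, 0.05 statistical tests, a sample size of 36 for each of the three groups", which makes 108 completed patients in all.

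The 24-hour reference mean and the 24-hour SD are not printed. Section 9.1 gives no reason for scaling either quantity from 48 to 24 hours and no range of power over other SDs. Section 9.2 plans a parametric ANOVA with pairwise comparisons for hydromorphone use.

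**The concern.** The window changes in the middle of the calculation. The mean is visibly halved, because 19.5 mg is 75% of 26 mg. The SD is never restated for 24 hours. If the printed 22 mg is put beside the 6.5 mg difference, about 142 per group are needed, so at first sight 36 looks far too small.

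On a closer look the SD must have been halved too, and that step is open to question. An SD does not in general shrink in proportion to the time window. If the two days had equal means and equal SDs, a 24-hour SD of 11 mg would require perfect correlation between a patient's use on day 1 and on day 2. Any weaker correlation would give a larger SD and power below 80%.

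The 80% is the only power figure in the plan and the only basis for the 108 completed patients. If it rested on an SD that was too small, the trial could miss a real 25% reduction more often than planned.

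**Working it through.** **Inputs from Section 9.1.** The 48-hour mean is 52 mg and the SD 22 mg; the 24-hour target is 19.5 mg after a 25% reduction; the test is one-sided at 0.05; power is 80%; there are 36 per group.

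**Implied 24-hour inputs.** Reference mean: 19.5/0.75 = 26 mg = 52/2. Difference: 26 − 19.5 = 6.5 mg. The SD is not printed.

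**Reproducing 36.** For two means, n per group = 2(z₀.₉₅ + z₀.₈₀)²(SD/difference)², with z values 1.645 and 0.842.

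- SD 11 mg (22/2): 2 × 2.487² × (11/6.5)² = 35.4, so 36. Power at 36 is 80.6% by normal approximation and 79.9% by exact two-group t test. With the pooled error of the three-group ANOVA (3 × 35 = 105 degrees of freedom) it is 80.1%.
- SD 22 mg: 2 × 2.487² × (22/6.5)² = 141.7, so 142.
- Solving backwards by the normal approximation, SDs between 10.94 and 11.09 mg return 36.

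The same 36 comes from the 48-hour scale without any halving: a 25% reduction of 52 mg is 13 mg, and 13/22 = 6.5/11 = 0.59. The calculation therefore carries the 48-hour coefficient of variation, 22/52 = 11/26 = 42%, over to 24 hours. The 22 mg is labelled as a 48-hour SD, so the 142 is no correction. It shows only that 22 mg was not used as the 24-hour SD.

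**How far power moves with the SD.** Exact two-group t test, 36 per group, difference 6.5 mg, common SD in both arms. SDs other than 11 mg are assumptions.

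| 24-hour SD (mg) | Power |
|---|---|
| 9 | 92% |
| 10 | 86% |
| 11 | 80% |
| 12 | 74% |
| 13 | 68% |

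**Which direction?** The inputs below (correlation ρ between days, ratio of daily SDs, day-1 share) are assumptions; the documents give none of them.

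- Even split, equal daily SDs: SD = 22/√(2(1+ρ)). For ρ = 1, 0.5 and 0 this is 11.0, 12.7 and 15.6 mg, with power 80%, 69% and 54%.
- Even split, ρ = 0.5, day-2 SD 1.5 times the day-1 SD: SD = 22/√(1 + 2.25 + 1.5) = 10.1 mg, power 86%.
- 70% of use on day 1, ρ = 0.5, equal daily SDs: difference 0.25 × 0.70 × 52 = 9.1 mg, SD 12.7 mg, power 91%.

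Plausible patterns fall on both sides of 80%.

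**The common-SD assumption.** The figures above give both arms the same SD. If both arms instead shared a coefficient of variation of 42%, the SDs would be 11 and 19.5 × 11/26 = 8.25 mg. The standard error is √((11² + 8.25²)/36) = 2.29 mg, and power is about 88%. On that footing 80% holds up to a coefficient of variation of about 48%. So 42% is a ceiling for 80% power only when the SD is common to both arms.

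**The case for a change.** The best case for a change is that the sole justification for 108 patients rests on a number the plan does not print. A reader has to work backwards to find 11 mg, and nothing in the documents supports it. With an even split and equal daily SDs, 11 mg is the smallest SD possible, so under that reading 80% is the most the trial could have. Between SDs of 9 and 13 mg the chance of missing a true 6.5 mg difference rises from 8% to 32%. The remedy would be a few sentences and no extra patients.

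Much of this stands. The 24-hour SD is unstated, the constant coefficient of variation is not defended, and a careful author would have written both down. Three things limit its weight. The even split with equal daily SDs is itself unsupported, and other patterns give more than 80%, so no loss of power is shown. The input can be recovered from the printed figures by simple division, and the result agrees with the stated 36. Finally, the planning SD does not govern how the result is read: the completed trial will supply its own 24-hour SD and confidence intervals, and a null result would be judged from those.

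The sizing in morphine rather than hydromorphone adds nothing to this point, because a constant conversion factor scales the difference and the SD alike.

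**Conclusion.** The concern describes a real gap in reporting but does not call for a change. Given a difference of 6.5 mg and a common 24-hour SD of 11 mg, 36 per group gives 79.9% to 80.6% power at one-sided 0.05, depending on the formula. That matches the plan. The arithmetic is sound; what is missing is one sentence saying that the 48-hour coefficient of variation of 42% was assumed to apply at 24 hours.

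Whether true power is above or below 80% cannot be settled from the documents, which give no 24-hour SD, no correlation between days and no day-1 share. The illustrations run from 54% to 92% and rest on assumed inputs. Stating the assumption would make Section 9.1 easier to follow, but it would leave the 36 per group, the ANOVA in Section 9.2 and the trial's conclusions as they are.

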### 9.2 Statistical methods

Our current plan is to use ANOVA, along with pairwise comparisons, to compare the three groups with respect to pain scores (nonparametric ANOVA) and total hydromorphone use (parametric ANOVA) in the first 24 hours post-operatively, to determine whether there are any significant differences. We will use SAS, Version 9.4, for all statistical analyses.

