### **1.2 Primary Study Endpoints**

1. Total hydromorphone use in 1st 24 hours post-operatively.

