### **1.3 Secondary Study Endpoints**

1. Pain Scores using Visual Analogue Scale (VAS) [ Time Frame: 1st 24 hours post-op ]
2. Sedation scores using Ramsey Sedation Scale [ Time Frame: 1st 24 hours post-op ]
3. Nausea Scores using PONV Impact Scale Score [ Time Frame: 1st 24 hours post-op ] – see data collection sheet
4. Intraoperative fentanyl use [ Time Frame: Intraoperative period ]
5. Intraoperative minimum alveolar concentration (MAC) of desflurane
6. Sentec CO2 measurements, average PCO2 will be taken every hour [Time Frame: 1st 24 hours post-op].

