#### **7.2.5 Post- op**

As per standard of care, the patient will be taken to the post anesthesia care unit (PACU) and set up with standard ASA monitoring as well as the Sentec CO2 monitor which was applied in the SDU.. A hydromorphone patient controlled analgesia (PCA) pump will be set-up by nursing and given to the patient. Standard dosing of 0.2 mg bolus, every 6 minutes with a maximum 2 mg per hour will be the starting dose as is standard for these patients post-operatively. As per standard of care, 1 gm of Tylenol every 8hrs will also be scheduled to be administered via IV route for 1st 24hrs. If reported pain scores are beyond the patients previously determined acceptable pain score (asked pre-operatively per hospital standard) the PACU resident may give additional doses of IV hydromorphone at his/her discretion. When patient meets discharge criteria they will be sent from the PACU to their room with monitoring of continuous pulse oximetry and ETCO2 until 24 hours post-operation.

During the post-operative period, data will be recorded immediately upon arrival to PACU and every 4 hours thereafter with a maximum recording of 24 hours post-op. For study purposes, a data sheet will be assigned to the patient pre-operatively with pre-operative pain anxiety, and PONV scores recorded. The sheet will then be attached to the patients chart and data recorded by the nursing staff. At the end of the 24 hour period the sheets will be collected by one of the research team members.

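### Section 9.2 compares hydromorphone use and pain scores without a covariate although pre-operative scores are recorded; prespecified adjustment is a cheap precision gain, possibly small, and not the repair of an error

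*Combined protocol and SAP*

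**What the plan says.** The primary endpoint is "Total hydromorphone use in 1 st 24 hours post-operatively" (section 1.2). Pain is the first secondary endpoint: "Pain Scores using Visual Analogue Scale (VAS) [ Time Frame: 1st 24 hours post-op" (section 1.3). Section 9.2 compares the three groups by ANOVA with pairwise comparisons on "pain scores (nonparametric ANOVA) and total hydromorphone use (parametric ANOVA) in the first 24 hours post-operatively". It mentions no covariate, no per-patient summary of the repeated pain scores and no rule for missing values.

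Section 7.2.5 states that "a data sheet will be assigned to the patient pre-operatively with pre-operative pain anxiety, and PONV scores recorded". It continues: "The sheet will then be attached to the patients chart and data recorded by the nursing staff". Post-operative data are taken on arrival in the PACU and then every 4 hours up to 24 hours. No section uses the pre-operative scores in an analysis. Sections 7.2.2 and 7.4.3 describe blocks of nine and name no stratification factor, so baseline information enters neither the allocation nor the analysis.

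Section 9.1 sizes the trial for "80% statistical power with one-sided, 0.05 statistical tests, a sample size of 36 for each of the three groups is needed", with a "total sample size of 108 completed patients for statistical analysis".

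**The concern.** The sample size meets its power target with almost nothing to spare, and for a single pairwise comparison. A baseline variable that predicts the outcome removes part of the residual variance at no cost in patients, and candidate variables are already being written down. If the choice is left until the data are open, any adjusted result will look selected. The choice therefore has to be made beforehand, if it is made at all.

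Precision in the two comparisons of section 9.2 is all that is at stake. Bias and type I error are not in question.

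**Working it through.** **Inputs.** Section 9.1 reports that "the mean (and standard deviation) for the 48-hour morphine use in the ketamine group was 52 mg + 22 mg". Halving the mean gives 26 mg for 24 hours. The combination is expected to reach 19.5 mg, so the difference is 26 − 19.5 = 6.5 mg. The 24-hour SD is not stated. Halving 22 gives 11 mg, and I use it because it reproduces the plan's own figure. These are milligrams of morphine; a constant conversion to hydromorphone leaves power unchanged.

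**The plan's figure.** n per group = 2(1.645 + 0.842)² × 11² / 6.5² = 35.4, rounded up to 36. This agrees with section 9.1.

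**Unadjusted power.** SE = 11 × √(2/36) = 2.593 and noncentrality = 6.5/2.593 = 2.507. With 105 df and one-sided 0.05, the noncentral t distribution gives 80.1%.

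**Adjusted power.** With k covariates that explain a fraction R² of the within-group variance, N = 108 and three groups:

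SE = 11 × √[(2/36) × (1 − R²) × (1 + k/(N − 3 − k − 1))], df = 105 − k.

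The last factor is the expected cost of chance imbalance in the covariates: 1 + 2/102 for two and 1 + 1/103 for one. The documents give no R², so the range is an assumption.

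| R² | SE, two covariates | Noncentrality | Power, two covariates | Power, one covariate |
|---|---|---|---|---|
| 0 | 2.618 | 2.483 | 79.4% | 79.8% |
| 0.05 | 2.552 | 2.547 | 81.2% | 81.5% |
| 0.10 | 2.484 | 2.617 | 83.0% | 83.3% |
| 0.20 | 2.342 | 2.776 | 86.7% | 87.0% |

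The break-even R² is about 0.02 with two covariates and about 0.01 with one. If the scores explain nothing, two covariates cost 80.1 − 79.4 = 0.7 points. Adding the PONV score as a third would bring power at R² = 0 to 79.1%, which is a reason to keep the list short.

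**Sidedness.** Section 9.2 states none. At two-sided 0.05, power is 70.0% unadjusted, against 69.1%, 71.3%, 73.7% and 78.5% at the same four R² values with two covariates. The pattern does not change.

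**Missing baseline scores.** The documents give no number, so this is only an illustration. If patients without scores were dropped, power at R² = 0 with two covariates would be 78.4% with one missing per group and 77.3% with two. If two per group were missing and filled with the overall mean, it would stay at 79.4%.

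**The case against.** The strongest objection is that no defect has been shown. The unadjusted ANOVA is valid under randomisation, it matches the sample size calculation, and no stratification factor calls for adjustment. All of that stands, and it limits the point to an optional improvement.

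The second is that the benefit is unproven. Nothing in the documents says that these scores predict opioid use, they are not a baseline of hydromorphone consumption, and section 3.2 excludes chronic opiate users, which may narrow baseline variation. At R² = 0.05 the gain is worth about one extra completer per group (37 per group unadjusted gives 81.1%). The 86.7% figure needs a multiple correlation of about 0.45. This stands too, and is why the gain has to be described as possibly small.

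The third is that the SD matters more. With an SD of 12 mg, power is 73.8% unadjusted and 75.0% adjusted at R² = 0.05; with 22/√2 = 15.56 mg it is 54.6% and 55.7%. Adjustment does not rescue an optimistic SD. That is correct, but it is a separate question.

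A reader might also infer that baseline scores will often be missing because nursing staff complete the sheet. Section 7.2.5 does not support this. Its natural reading is that the pre-operative scores are entered first, the sheet then goes to the chart, and nursing staff record what follows. The text neither states nor implies how many baseline scores will be missing, so a missing-score rule is only a precaution.

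**Conclusion.** The point holds as a low-cost suggestion. Section 9.2 leaves recorded baseline scores unused. For hydromorphone, prespecified adjustment changes power by between −0.7 and +6.6 points (86.7 − 80.1) over an assumed R² of 0 to 0.20, and by +1.1 to +2.9 points at R² of 0.05 to 0.10. These figures rest on the 6.5 mg difference, the inferred SD of 11 mg, 36 completers per group and one-sided 0.05.

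The argument is stronger for pain, where the covariate is a pre-operative score of the same symptom. That adjustment cannot be applied, however, until the plan says how the 4-hourly scores become one value per patient.

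Two stronger readings should be resisted: that the planned ANOVA is wrong, and that adjustment would materially strengthen the trial. The first is false under randomisation; the second needs an R² that the documents do not supply.

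**What to change.** Before unblinding:

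1. Check the data sheet to see whether pre-operative pain and anxiety are two scores or one; the punctuation in section 7.2.5 leaves this open. Then prespecify an ANCOVA of 24-hour hydromorphone on group with both scores as covariates (one covariate if it is a single score), and report the unadjusted ANOVA alongside. State which of the two carries the primary conclusion. Either is defensible, but the adjusted power figures apply only if it is the ANCOVA.
2. Define one per-patient summary of the 4-hourly pain scores, such as the 24-hour mean, and adjust its comparison for the pre-operative pain score, for example by rank ANCOVA.
3. As a precaution, fill any missing baseline score without regard to group, for example by the overall mean, so that no completer is dropped.

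The cost is a few lines in section 9.2 and a look at the data sheet. No new data are needed. The statistical price is two degrees of freedom, about 0.7 points of power if the scores turn out to explain nothing.

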## 10.0 Confidentiality, Privacy and Data Management

See Research Data Plan form.

## 11.0 Data and Safety Monitoring Plan

### 11.1 Periodic evaluation of data

The PI and research coordinator will review cumulative adverse events, early termination of study participation, and accrual every six months and report any issues requiring modification of the study or alteration of the risk: benefit ratio to the IRB immediately. A summary of adverse events, study progress and protocol modifications will be included for IRB review in the continuing review.

### 11.2 Data that are reviewed

The data to be reviewed will be:

- Safety data
- Untoward events
- Efficacy data

### 11.3 Method of collection of safety information

Safety information will be collected by the research staff preoperatively and post operatively as described in Section 7.2.

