#### **7.2.4 Day of Surgery Pre-Operation and Operating Room**

During routine check of preoperative vital signs in the SDU the patient will be fitted with the Sentec CO2 monitor. Standard preoperative checklists/questions will be asked by the nursing staff as per hospital protocol.

The investigational pharmacy will deliver the appropriate study medication to the OR window, or the drug will be picked up by the coordinator at the investigational pharmacy. Prior to induction of anesthesia the patient will receive 1-2 mg of IV midazolam for anxiolysis if needed. Anesthesia will be induced with propofol (1.5-2.5 mg/kg) and fentanyl 1-2 $\mu$ g/kg. Muscle relaxant will be administered to facilitate tracheal intubation and to maintain muscular relaxation. Following securement of the endotracheal tube, the study medication will be administered over 10 minutes via an IV infusion pump. Dexamethasone 4 mg and 1 gm of Tylenol IV will be given after the study medication has been delivered, as per standard of care. Maintenance of anesthesia will be with desflurane and fentanyl dosing at the discretion of the primary team. End tidal CO2 will be maintained between 30-35 mm hg (Apollo SW4.5n, Anesthetic Gas Module, Telford,PA, USA). No long-acting opiate will be used. 4 mg ondansetron will be given during skin closure at the end of surgery. Subjects will then be fully reversed and allowed to emerge from anesthesia and will be extubated per the primary anesthesia team. The above protocol is standard care for a patient undergoing a sleeve gastrectomy. The only non-standard part of this anesthetic is the addition of the study medications.

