### 11.4 Frequency of data collection

Data will be collected immediately post-op, and every 4 hours thereafter, until 24 hours post-op, on the day of surgery.

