## 12.0 Risks

Risks specific to this study include:

- Risk of randomization - patient will be assigned to a treatment program by chance. The treatment received may prove to be less effective than the other research treatment(s) or other available treatments.
- Loss of confidentiality associated with being part of a research study collecting personal health information.
- Ketamine adverse effects at proposed dosing include:
  - Uncommon: hypertension, increased cardiac output, increased intracranial pressure, tachycardia, tonic-clonic movements, visual hallucinations, vivid dreams, bradycardia,

diplopia, hypotension, increased intra-ocular pressure, injection-site pain, nystagmus, anaphylaxis, cardiac arrhythmia, depressed cough reflex, fasciculations, hyper salivation, increased metabolic rate, hypertonia, laryngospasm.

- Magnesium adverse effects at proposed dosing include:
  - Uncommon: flushing, drowsiness, circulatory collapse, respiratory paralysis, hypothermia, pulmonary edema, depressed reflexes, hypotension, depressed cardiac function, diaphoresis, hypocalcemia, hypophosphatemia, hyperkalemia, visual changes.
- Adverse effects related to the study medications at proposed dosing are uncommon. Most adverse effects noted were at higher dosing; there is limited literature noting adverse effects at proposed dosing.

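### The scheduled safety collection skips the intra-operative period in which both study drugs are infused, leaving capture there to unscheduled reporting

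*Combined protocol and SAP*

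**What the plan says.** Section 11.3 sets the method of safety collection: "Safety information will be collected by the research staff preoperatively and post operatively as described in Section 7.2". Section 11.4 sets the frequency: "Data will be collected immediately post-op, and every 4 hours thereafter, until 24 hours post-op, on the day of surgery". Section 7.2.5, the post-operative part of the section that 11.3 points to, says that "data will be recorded immediately upon arrival to PACU and every 4 hours thereafter with a maximum recording of 24 hours post-op".

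The exposure is described in Section 7.2.4: "Following securement of the endotracheal tube, the study medication will be administered over 10 minutes via an IV infusion pump". Section 7.4.6.3 repeats this. Maintenance, emergence and extubation follow, and only then transfer to the PACU.

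Section 12 introduces one list with "Ketamine adverse effects at proposed dosing include", which begins "Uncommon: hypertension, increased cardiac output, increased intracranial pressure, tachycardia, tonic-clonic movements, visual hallucinations, vivid dreams, bradycardia" and goes on to hypotension, anaphylaxis and cardiac arrhythmia among others. The magnesium list includes hypotension and circulatory collapse. Neither list gives a time of onset.

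Safety data are among the data to be reviewed (11.2), and cumulative adverse events are reviewed every six months (11.1, 11.6).

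**The concern.** The study drugs are what distinguishes the three arms, and Section 7.2.4 itself describes them as the only departure from standard anesthetic care. A safety schedule would be expected to cover the time when they are running and the period just afterwards. The schedule stated here has a pre-operative part and a post-operative part with nothing between them, and the infusions fall in the space between.

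What is at stake is how even and complete the safety comparison is. Section 12 says there is little literature on adverse effects at these doses, so a blinded, placebo-controlled trial could add useful comparative information. It can do so only if events are sought in the same way in every arm. Where capture depends on someone choosing to report an event, differences between arms mix true differences with differences in reporting. The six-monthly review of risk and benefit would then rest on those counts.

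**Working it through.** The point is one of timing, so the check sets the stated schedule beside the stated exposure and then tests whether any other section covers the difference.

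1. **Scheduled points.** From 7.2.5 and 11.4: one on PACU arrival, then every 4 hours to 24 hours. 24 / 4 = 6, and 6 + 1 = 7 post-operative points, at 0, 4, 8, 12, 16, 20 and 24 hours. Section 11.3 adds pre-operative collection.

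2. **Exposure.** From 7.2.4 and 7.4.6.3: 10 minutes of infusion after intubation, hence after the pre-operative collection and before PACU arrival. Scheduled safety points between the start of infusion and PACU arrival: 0.

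3. **The cross-reference.** Section 11.3 relies on 7.2 for its method. Section 7.2.4, which covers the operating room, describes drugs, an end-tidal CO2 target and extubation. It names no safety item to be recorded during infusion, maintenance or emergence.

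4. **Other routes by which an intra-operative event could enter the data.**
   - Section 21.2 has no time limit, but it deals with events seen by or reported to the study team and believed to be drug-associated. It is passive and filtered by a causality judgment.
   - Section 21.6 has the anesthetic provider trigger unblinding for instability or a possible reaction. It is not a recording rule, and events that enter this way arrive with the allocation known.
   - Section 3.3.1 removes patients whose hemodynamics change by more than 20% after induction, which requires intra-operative values to be looked at. Section 3.3.2 then follows opiate use, pain scores and vital signs for 24 hours, but does not say that the triggering change is recorded as a safety event.
   - Section 22.1.2 shows that adverse event forms exist and that the principal investigator checks them. It does not say what intra-operative source feeds them.

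5. **Which risks are touched.** Section 12 lists 21 effects for ketamine and 14 for magnesium, 21 + 14 = 35 entries, with onset times for none. Hypertension, hypotension, tachycardia, bradycardia, arrhythmia and anaphylaxis could occur during an infusion. Hallucinations, vivid dreams, diplopia, drowsiness and visual changes depend largely on an awake patient, so they would mostly surface inside the post-operative schedule.

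6. **Patients concerned.** Two of three arms receive active drug: 2 x 36 = 72 of the 108 planned completers (9.1). This is the number exposed in the unscheduled interval, not a number of missed events.

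No figure in the plan depends on this point. The 36 per group in 9.1 rests on opioid consumption and does not change.

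**The case against.** The strongest reply is that intra-operative events are not lost. Section 21.1 defines an adverse event whether or not it is thought drug-related, 22.1.2 has all adverse events entered on forms with no time window, and 21.6 and 3.3.1 are directed at just the instability and hemodynamic change of most interest. Section 11.4 is also not a complete list of data collection: intra-operative fentanyl and desflurane concentration are secondary endpoints (1.3), and 11.4 omits those too. The trial has no safety endpoint or safety hypothesis.

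Much of this stands, and it rules out several stronger readings that a reader might infer:

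- That safety data are collected only before and after surgery. The routes above allow event-driven capture in between. What is missing is scheduled collection.
- That most Section 12 risks fall in the gap. Without onset times the documents support no more than several.
- That hallucinations and vivid dreams are never asked about. The data collection sheet is not shown. The pain, anxiety and PONV scores named in 7.2.5 are its pre-operative entries, not a list of its contents. Sedation scores and CO2 measurements (1.3) also bear on drowsiness and respiratory effects.
- That reported rates would be near zero in all arms. This is conjecture, because unscheduled capture is less systematic but not absent.
- That 11.3 and 7.2.5 conflict over who collects the data. Section 7.2.5 says "The sheet will then be attached to the patients chart and data recorded by the nursing staff", and a research team member then gathers the sheets. The two statements are compatible.

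The reply does not supply a statement of which intra-operative safety data are recorded, when, or by whom. That intra-operative fentanyl and desflurane data are taken shows that adding safety items is feasible, not that they are already taken.

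**Conclusion.** The concern holds as a gap in scheduled safety ascertainment. The stated schedule has 7 post-operative points and none between the start of infusion and PACU arrival, so capture during the exposure depends on unscheduled reporting. Several listed hemodynamic, rhythm and allergic events may be under-recorded and not comparable across arms. The documents give no event rates, so the extent cannot be estimated.

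The conclusion assumes that 11.3 and 11.4 are followed as written and that no document outside this text, such as the data sheet, already requires intra-operative safety items. The primary endpoint, its analysis and the sample size are unaffected. The plan should be changed on this point, but the main question of the trial does not depend on it.

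**What to change.** Amend 11.3 and 11.4 so that safety collection runs from the start of the study-drug infusion. Up to PACU arrival, extract from the anesthesia record blood pressure, heart rate, rhythm events, treatments given for them and any interruption of the infusion. Do this in all patients, with the same form in all three arms and by someone blinded to allocation, including for patients unblinded under 21.6. Tabulate the results by arm.

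Check the data collection sheet. If it has no such item, add a yes/no line for the Section 12 effects, including hallucinations and vivid dreams, at the existing 4-hourly points.

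The cost is one extraction page, possibly a few tick boxes, and a few minutes of coordinator and nurse time per patient. No new procedure or assessor is needed and clinical management does not change. This assumes that the routine anesthesia record holds these items, which is likely since the trial already needs intra-operative fentanyl and desflurane data.
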